**Figure 5.1-1: Study Design Schematic Part 1 and Part 2**

The analysis of the primary endpoint ORR will take place after the last treated subject is followed for at least 6 months. Additional survival analysis will be conducted with longer follow-up.

The analysis of the primary endpoint ORR for Part 2 will take place after at least 150 subjects are followed for at least 6 months. Additional survival analysis will be conducted with longer follow-up.

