## 5 STUDY DESIGN

### 5.1 Overall Design

Protocol CA209592 is an open-label, exploratory Phase 2 trial evaluating nivolumab combined with ipilimumab in participants  $\geq$  18 years old with histologically confirmed advanced or metastatic NSCLC, with no prior systemic anticancer therapy given as primary therapy for advanced disease.

In Part 1, participants will undergo screening evaluations to determine eligibility within 28 days prior to treatment assignment, and approximately 100 patients will be treated with at least 50 PD-L1 positive patients and 50 PD-L1 negative patients. Tumor sample for PD-L1 status assessment is required at screening.

Upon determination of PD-L1 status (cut-off of 1%), 2 cohorts will be defined: PD-L1 positive and negative, and patients in each cohort will receive nivolumab + ipilimumab.

[figure not shown]
In Part 2, approximately 150 participants will be treated with nivolumab + ipilimumab regardless of their PD-L1 status.

All participants (Part 1 and Part 2) will be treated with the following:

- nivolumab 240mg IV every 2 weeks + ipilimumab 1 mg/kg IV every 6 weeks until disease progression, unacceptable toxicity, withdrawal of consent, the study ends, or a maximum treatment duration of 2 years, whichever occurs first. Participants will be permitted to continue on nivolumab +/- ipilimumab beyond initial RECIST 1.1 defined progression, as long as they meet the criteria described in [Section 8.1.2](#).

The study design schematic is presented in [Figure 5.1-1](#).

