### **5.2 Number of Participants**

**Part 1:** The planned sample size is approximately 100 patients. Approximately up to 150 participants are expected to be enrolled to achieve 100 treated participants in the trial. For this hypothesis-generating study, the sample size is mainly decided by operational feasibility. No formal hypothesis testing will be conducted. Participation in Part 1 is restricted to sites in the US.

**Part 2:** Approximately 200 participants are expected to be enrolled to achieve 150 treated participants. Sites in US and Europe may participate in Part 2.

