### 10.3 Statistical and Computational Analyses

The association between ORR and tumor mutational burden will be explored using logistic regression model among treated patients evaluable for tumor mutational burden.

Due to limited participants as compared with the number of biomarkers that will be evaluated for the second co-primary objective, a multiple logistic regression model, or penalized regression methods (Elastic Net, implemented in SAS procedure GLMSELECT) will be used to assess the potential association between candidate biomarkers in peripheral blood and tumor tissue at baseline and on-treatment with clinical efficacy measures. The primary endpoint will be ORR, and other clinical efficacy measures will be analyzed as part of the secondary endpoints.

The analysis of the primary endpoint ORR will take place after the last treated subject is followed for [REDACTED]. Additional survival analysis will be conducted with longer follow up.

The statistical analysis plan will be developed and finalized before database lock and will describe the selection of participants to be included in the analyses, and procedures for accounting for missing, unused, and spurious data. Below is a summary of planned statistical analyses of the primary and secondary endpoints.

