### 3.3.4 Confirmation Scans

Verification of Response: To be assigned a status of CR or PR, changes in tumor measurements must be confirmed by consecutive repeat assessments that should be performed no less than 28 days after the criteria for response are first met. For this study, the next scheduled tumor assessment can meet this requirement.

Verification of Progression: Progression of disease should be verified in cases where progression is equivocal. If repeat scans confirm PD, then progression should be declared using the date of the

initial scan. If repeat scans do not confirm PD, then the subject is considered to not have progressive disease.

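### The Part 2 ORR trigger sets a hard floor of 150 against a planned number of about 150, and its 6-month minimum ends before a response first seen at Week 24 can be confirmed

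*Combined protocol and SAP*

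**What the plan says.** **Timing.** Two timing sentences follow Figure 5.1-1 in Section 5.1. One names no Part: "The analysis of the primary endpoint ORR will take place after the last treated subject is followed for at least 6 months". The other is specific to Part 2: "ORR for Part 2 will take place after at least 150 subjects are followed for at least 6 months". Section 10.3 repeats the first form, again without naming a Part: "The analysis of the primary endpoint ORR will take place after the last treated subject is followed for", with the length of follow-up redacted. The visible text does not say whether follow-up means time since first dose or time actually observed.

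**Size.** Section 5.1 states that in Part 2 "approximately 150 participants will be treated with nivolumab + ipilimumab regardless of their PD-L1 status". Section 5.2 adds: "Approximately 200 participants are expected to be enrolled to achieve 150 treated participants". Section 10.1 gives the same planning figures.

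**Endpoint.** Section 4 defines ORR on confirmed CR or PR. Appendix 6, Section 3.3.4, says that a response "must be confirmed by consecutive repeat assessments that should be performed no less than 28 days after the criteria for response are first met", and allows the next scheduled scan to serve. Section 9.1.1.1 schedules scans every 8 weeks (±1 week) from first dose for the first 12 months. Section 5.6 puts median time to response at 2-4 months.

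**The concern.** The trigger fixes the data set for the Part 2 primary endpoint, so it should have one meaning and suit the endpoint it serves.

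On the first count, an approximate target has become an exact minimum. If Part 2 closes slightly short, the rule as written is never satisfied and someone must decide when to cut. If it closes slightly over, the rule can be satisfied while the last participants are still short of 6 months. The study is open-label and has no data monitoring committee (Section 5.1.1), so the timing is better settled in advance.

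On the second count, the minimum follow-up does not leave room for the confirmatory scan after Week 24. A participant whose response is first seen at that scan, and who is near the minimum at the cut, is counted as a non-responder. Response status is also the outcome in the Part 2 ROC analysis and logistic regression on TMB (Section 10.3.1).

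**Working it through.** **The plan's own arithmetic.** The plan gives no calculation for the trigger. The one visible calculation that uses the Part 2 total is in Section 10.1: 250 × 60% × 1/3 = 50 participants above the TMB cutpoint. With 100 + 150 = 250 it reproduces.

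**Step 1: the floor of 150.** Take follow-up as time since first dose and let N be the number treated in Part 2.
- N ≤ 149: the condition is never met.
- N = 150: it is met when the last treated participant reaches 6 months. This agrees with the last-treated-subject rule.
- N > 150: it is met when the 150th reaches 6 months. The N − 150 treated later may have less.

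At a 6-month minimum, the two rules give the same date by construction only at N = 150.

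**Step 2: the confirmation window.** Days are counted from first dose.
- Six months = 6 × 365.25 / 12 = 182.6 days = 26.1 weeks.
- Scheduled scans: Weeks 8, 16, 24 and 32.
- Latest first response that can be confirmed by 6 months: (182.6 − 28) / 7 = Week 22.1.

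| First response seen | Earliest confirmation (+28 days) | Days after 6 months |
|---|---|---|
| Week 23 (early edge) | Day 161 + 28 = 189 | 6 |
| Week 24 | Day 168 + 28 = 196 (Week 28) | 13 |
| Week 25 (late edge) | Day 175 + 28 = 203 | 20 |

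On schedule, a Week 24 response is confirmed at Week 32, Day 224. A Week 16 response can be confirmed at Week 24. So for a participant at exactly 6 months, only first responses at the Week 8 and Week 16 scans can count. Under Table 3.3.3-1 in Appendix 6, a PR with no evaluable later scan is scored SD or NE.

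**Step 3: size.** The documents do not give the inputs, so these are assumptions: ORR 40%; 10-20% of responses first seen at Week 24; uniform accrual over 6 to 18 months (182.6 to 547.9 days); confirmation at the Week 32 scan. The participants affected have between Day 182.6 and Day 224 of follow-up at the cut, a span of 41.4 days.

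Loss in ORR = ORR × share first seen at Week 24 × (41.4 / accrual days)
- Low: 0.40 × 0.10 × 41.4 / 547.9 = 0.003, or 0.3 points.
- High: 0.40 × 0.20 × 41.4 / 182.6 = 0.018, or 1.8 points.

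In 150 participants that is 150 × 0.003 = 0.45 to 150 × 0.018 = 2.7 responders.

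**Step 4: effect in the TMB-high subgroup.** If the 60% and 1/3 of Section 10.1 are applied to Part 2 alone (an assumption), 150 × 0.60 / 3 = 30 participants are above the cutpoint. One misclassified responder there moves that ORR by 1/30 = 3.3 points.

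**The case against.** The strongest reply is that little is at stake.
- An approximate target is not a cap, and about 200 are to be enrolled to reach 150 treated, so the floor may well be met.
- A general rule followed by a Part 2 rule is not necessarily a contradiction, and the follow-up length in 10.3 is redacted.
- Section 10.2 defines the treated and TMB-evaluable populations, so the trigger need not exclude anyone treated after the 150th.
- Six months is a minimum, so earlier participants have longer follow-up, and most responses are expected by 2-4 months.
- The under-count is small beside sampling error: the exact 95% CI at an observed 40% is 32-48% for n = 150 and 23-59% for n = 30.
- No hypothesis is formally tested (Section 3.2.6), and any cut leaves its own last scan unconfirmed.

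Most of this stands, and it limits the point. A reader might infer that the trigger cannot be reached at all, because some participants will die or withdraw before 6 months. The documents do not support that. The neighbouring sentence uses the same verb for the last treated subject, and on that reading a whole analysis would depend on one person surviving 6 months. Time since first dose is the natural meaning in both places.

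The reply does not remove two things: a minimum with no margin against an approximate target, and an under-count that runs only downward and follows from the plan's own scan and confirmation rules.

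**Conclusion.** The point holds in a limited form. The Part 2 trigger is reachable, but it has no margin, does not define follow-up, and matches the last-treated-subject rule only if exactly 150 are treated. It should not be called impossible, nor a proven contradiction with Section 10.3. Section 10.3.5 on interim analyses, cited in the summary of changes, is not in the text available and could not be checked.

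The confirmation gap is certain as arithmetic, including at the edges of the ±1 week window. Its effect on ORR is small, about 0.3 to 1.8 points under the assumed ORR, late-response share and accrual, and it falls only on participants near the minimum at the cut. The documents do not show that it distorts the association between TMB and response, which is the Part 2 primary objective. It is worth correcting because the direction of the bias is known and the remedy is cheap.

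**What to change.** Use one rule for Part 2 in both 5.1 and 10.3: the ORR analysis takes place when the last treated Part 2 participant has passed the Week 32 (+1 week) assessment, or has progressed, died or left tumour follow-up earlier, and all treated Part 2 participants are included. Apply the condition to every participant, so that an early exit by the last one treated does not bring the cut forward for the others.

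This removes the floor of 150, makes clear what follow-up means, and lets a Week 24 response be confirmed on the existing scan schedule.

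Cost: wording in two sections and a later cut. Week 32 is 224 − 182.6 = 41.4 days (5.9 weeks) after 6 months, and Week 33 is 231 − 182.6 = 48.4 days (6.9 weeks) after. That compares with about 48 months from start of enrollment to the primary analysis (Section 5.3). The remaining limit is that a response first seen at Week 32 in the last-treated participants would still be unconfirmed. The report should say so.

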### **5.1.1 Data Monitoring Committee and Other External Committees**

A Data Monitoring Committee (DMC) will not be utilized for this study, given the following:

- 1) This study is an open-label study.
- 2) Data from the ongoing Phase I CA209012 study has demonstrated a favorable benefit/risk profile and a manageable safety that is consistent with prior experience with these agents.
- 3) Safety data will be closely monitored by BMS, with real time review and assessment of SAEs as they are received, and periodic review of all adverse events data for potential new safety signals.

### **5.2 Number of Participants**

**Part 1:** The planned sample size is approximately 100 patients. Approximately up to 150 participants are expected to be enrolled to achieve 100 treated participants in the trial. For this hypothesis-generating study, the sample size is mainly decided by operational feasibility. No formal hypothesis testing will be conducted. Participation in Part 1 is restricted to sites in the US.

**Part 2:** Approximately 200 participants are expected to be enrolled to achieve 150 treated participants. Sites in US and Europe may participate in Part 2.

### **5.3 End of Study Definition**

The duration of the study from start of enrollment to analysis of the primary endpoint is expected to be approximately 48 months. The study will end once additional survival follow-up has concluded.

#### **5.4 Scientific Rationale for Study Design**

Clinical activity of nivolumab and ipilimumab combination has shown superior efficacy over monotherapy in different tumor types including NSCLC. Although efficacy is superior in PD-L1 positive patients, responses were also observed in subjects with tumors that are not expressing PD-L1 ligand.

Unfortunately, not all patients will respond to immune checkpoint blockade, therefore there is the need for a better understanding of factors that can predict response and progression.

CA209592 study has been designed to explore the immunomodulatory and pharmacodynamic activity of nivolumab and ipilimumab, and potential biomarkers/signatures correlated with response and safety in both PD-L1 positive and negative subjects.

#### **5.5 Justification for Dose**

The dose and schedule of nivolumab and ipilimumab in this trial was selected in part based on the data observed in the CA209012 study, which demonstrated activity of the combination of nivolumab 3 mg/kg every 2 weeks plus ipilimumab 1 mg/kg every 6 weeks in both PD-L1+ and PD-L1- tumors, coupled with a manageable safety profile.

Nivolumab flat dosing offers several advantages over body weight normalized dosing, including reduced potential for dosing errors and shortened dosage preparation time. A flat dose of 240 mg every 2 weeks is expected to produce the equivalent average exposure to 3 mg/kg every 2 weeks at the median body weight of ~80 kg in nivolumab-treated participants.

CA209-592 will include nivolumab 240mg every 2 weeks plus ipilimumab 1 mg/kg every 6 weeks.

#### **5.6 Duration of Treatment with Nivolumab plus Ipilimumab**

The optimal duration of immunotherapy is an important question and continues to be investigated. Clinical trials across different tumor types in the nivolumab and ipilimumab development program indicate that most of the responses occur early, with a median time to response of 2-4 months, and emerging data suggests that benefit can be maintained in the absence of continued treatment. A recent analysis in a melanoma study suggests the majority of patients who discontinue nivolumab and/or ipilimumab for toxicity maintain disease control in the absence of further treatment. Furthermore, a limited duration of ipilimumab, including only 4 induction doses, resulted in long term survival in patients with metastatic melanoma, with a sustained plateau in survival starting around 2 years after the start of treatment.

Accumulating data suggest that 2 years of PD-1 checkpoint inhibitor treatment may be sufficient for long term benefit. CA209003, a dose-escalation cohort expansion trial evaluating the safety and clinical activity of nivolumab in patients with previously treated advanced solid tumors (including 129 subjects with NSCLC), specified a maximum treatment duration of 2 years. Among 16 subjects with non-small cell lung cancer (NSCLC) who discontinued nivolumab after completing 2 years of treatment, 12 subjects were alive >5 years and remained progression-free without any subsequent therapy. In the CA209003 NSCLC cohort, the overall survival (OS) curve begins to plateau after 2 years, with an OS rate of 25% at 2 years and 18% at 3 years. These

survival outcomes are similar to phase 3 studies in previously treated NSCLC, in which nivolumab treatment was continued until progression or unacceptable toxicity (2 year OS rates of 23% and 29%, and 3 year OS rates of 16%-18% for squamous and non-squamous NSCLC respectively).

Similar results have been reported in clinical studies of pembrolizumab, another PD-1 inhibitor. Keynote-010 was a randomized phase 3 trial of pembrolizumab (at either 2 mg/kg or 10 mg/kg every 3 weeks) versus docetaxel in subjects with previously treated, PD-L1-positive, advanced NSCLC which specified a maximum treatment duration of 2 years for pembrolizumab. OS was significantly longer with both pembrolizumab 2 mg/kg (HR = 0.72, p = 0.00017) and pembrolizumab 10 mg/kg (HR = 0.60, p < 0.00001) compared to docetaxel, with an OS plateau developing beyond 2 years in both pembrolizumab arms. Among 690 patients who received pembrolizumab, 47 patients completed 2 years of pembrolizumab and stopped treatment. Most were able to maintain their response, including those with stable disease, with only 2 patients (4%) having confirmed progression after stopping at 2 years.

Keynote-006 was a randomized phase 3 study of pembrolizumab versus ipilimumab in patients with advanced melanoma, which also specified a maximum 2 year duration of pembrolizumab treatment. 104 (19%) of 556 patients randomized to pembrolizumab completed 2 years of treatment. With a median follow-up of 9 months after completion of pembrolizumab, the estimated risk of progression or death was 9% in these patients.

Taken together, these data suggest that treatment beyond 2 years is unlikely to confer additional clinically meaningful benefit and that the risk of progression after discontinuing treatment at 2 years is low.

In contrast, a shorter duration of nivolumab of only 1 year was associated with increased risk of progression in previously treated patients with NSCLC, suggesting that treatment beyond 1 year is likely needed. In CA209153, patients with previously treated advanced NSCLC who completed 1 year of nivolumab therapy were randomized to either continue or stop treatment, with the option of retreatment upon progression. Among 163 patients still on treatment at 1 year and without progression, those who were randomized to continue nivolumab had significant improvement in progression-free survival (PFS) compared to those who were randomized to stop treatment, with median PFS (post-randomization) not reached vs 10.3 months, respectively; HR=0.42 (95% CI, 0.25 to 0.71). With a median follow-up of 14.9 months post-randomization, there also was a trend for patients on continued treatment to live longer (OS HR = 0.63 [95% CI: 0.33, 1.20]). Of note, the PFS curves in both groups plateau approximately 1 year after randomization (ie, 2 years after treatment initiation), suggesting that there may be minimal benefit in extending treatment beyond a total of 2 years.

Collectively, these data suggest that there is minimal if any benefit derived from continuing I-O treatment beyond two years in advanced tumors. However, even though immunotherapy is well tolerated, patients will be at risk for additional toxicity with longer term treatment. Therefore, in this study, treatment will be given for a maximum of 2 years from the start of study treatment.

## 6 STUDY POPULATION

For entry into the study, the following criteria MUST be met.

### 6.1 Inclusion Criteria

#### 1) Signed Written Informed Consent

- a) Participants must have signed and dated an IRB/IEC approved written informed consent form in accordance with regulatory and institutional guidelines. This must be obtained before the performance of any protocol related procedures that are not part of normal participant care.
- b) Participants must be willing and able to comply with scheduled visits, treatment schedule, and laboratory testing.

#### 2) Type of Participant and Target Disease Characteristics

- a) Subjects with histologically confirmed Stage IV or recurrent NSCLC (per the 7th International Association for the Study of Lung Cancer classification [Goldstraw 2007]), squamous or non-squamous histology, with no prior systemic anticancer therapy (including EGFR and ALK inhibitors) given as primary therapy for advanced or metastatic disease.

Prior adjuvant or neoadjuvant chemotherapy is permitted as long as the last administration of the prior regimen occurred at least 6 months prior to enrollment.

Prior chemoradiation for locally advanced disease is also permitted as long as the last administration of chemotherapy or radiotherapy (which ever was given last) occurred at least 6 months prior to enrollment.

- b) Measurable disease by CT or MRI per RECIST 1.1 criteria. Tumor assessment performed within 28 days of start of study treatment.
- c) All participants must have tissue submitted during screening. This may include either a formalin-fixed paraffin-embedded (FFPE) tissue block or a minimum of 15 unstained tumor tissue slides.

**Part 1:** For cohort assignment purposes (PD-L1 status determination), archival tissue samples  $\leq$  3 months old will be allowed to determine PD-L1 IHC results. Fresh pre-dose biopsy samples (5 cores: 3 in FFPE and 2 in HypoThermosol®) will still need to be submitted.

**Part 2:** a fresh biopsy (preferred) or archival sample ( $\leq$  3 months old) is required for enrollment, but treatment may start before test results are received.

- d) ECOG Performance Status 0 or 1.

#### 3) Age and Reproductive Status

- a) Males and Females, ages 18 years (or age of majority) and older.
- b) Women of childbearing potential (WOCBP) must have a negative serum or urine pregnancy test (minimum sensitivity 25 IU/L or equivalent units of HCG) within 24 hours prior to the start of study treatment.
- c) Women must not be breastfeeding.
- d) Women of childbearing potential (WOCBP) must agree to follow instructions for method(s) of contraception ([Appendix 4](#)) for the duration of treatment followed by a period of 30 days (duration of ovulatory cycle) plus the time required for the investigational drug to undergo five half-lives. WOCBP treated with nivo + ipi combination should use an

- adequate method to avoid pregnancy for 5 months (30 days plus the time required for nivolumab to undergo five half-lives) after the last dose of investigational drug.
- e) Males who are sexually active with WOCBP must agree to follow instructions for method(s) of contraception ([Appendix 4](#)) for the duration of treatment followed by a period of 90 days (duration of sperm turnover) plus the time required for the investigational drug to undergo five half-lives. Males treated with nivo + ipi combination who are sexually active with WOCBP must continue contraception for 7 months (90 days plus the time required for nivolumab to undergo five half-lives) after the last dose of investigational drug. In addition, male participants must be willing to refrain from sperm donation during this time.
  - f) Azoospermic males are exempt from contraceptive requirements. WOCBP who are continuously not heterosexually active are also exempt from contraceptive requirements, and still must undergo pregnancy testing as described in this section.

Investigators shall counsel WOCBP, and male participants who are sexually active with WOCBP, on the importance of pregnancy prevention and the implications of an unexpected pregnancy. Investigators shall advise on the use of highly effective methods of contraception, ([Appendix 4](#)) which have a failure rate of < 1% when used consistently and correctly.

